## 5.4 CONTRAINDICATIONS TO FURTHER VACCINATION

The following AEs constitute absolute contraindications to further administration of the study vaccine:

- Serious adverse event, severe adverse event (grade 3) or IME after vaccination considered to be consistent with a causal association to any of the study vaccines.
- Known hypersensitivity to any component of the vaccine or any antibiotic or severe reaction following previous administration of the vaccine.
- Acute severe febrile illness on the day of vaccination deemed by the Investigator to be a contraindication for vaccination.
- Diagnosis between 2 visits of any of the following medical conditions:
  - Uncontrolled severe chronic disease (see above under exclusions).
  - Coagulopathy.
  - Congenital or acquired immunodeficiency syndrome.
  - Acute flaccid paralysis (to be investigated as a SAE).

If any of these AEs occur during the study, and the subject is in a group scheduled to receive a second nOPV2 vaccination, the subject should not receive the second dose of vaccine but may continue other study procedures at the discretion of the Investigator. The subject will be followed until resolution of the event and to determine the immune response.

## 5.5 ADDITIONAL CONSTRAINTS

Information on prohibited therapies can be found in Section 7.

## **6. VACCINES**

Study vaccines: novel monovalent OPV type 2 (nOPV2) candidates 1 and 2 are produced by Bio Farma, Indonesia. Lots used will be nOPV2 candidate 2 (lot 2016), **nOPV2 candidate 1 (lot 2018) and nOPV2 candidate 2 (lot 2018)**.

Other vaccines: licensed bOPV and IPV for pre-vaccination of subjects in infant cohorts B prior to administration of the study vaccine. DTPw-HB-Hib will be provided by the sponsor. Pneumococcal conjugate and Rotavirus vaccines will be provided by the local National Immunization Program.

### **6.1 PHYSICAL DESCRIPTION OF THE STUDY VACCINES**

The nOPV2 candidate vaccines will be provided to the sites in vials presented as an aqueous yellow-red solution for oral use. Vials will be filled at concentrations for each candidate so that each dose of the nOPV2 vaccine candidate 1 (2018) and nOPV2 vaccine candidates 2 (2016 and 2018) will contain approximately  $10^6$  or  $10^5$  CCID50, dependent on study group. Both vaccines will be administered orally.

### **6.2 CHARACTERIZATION OF VACCINE LOTS**

In mouse neurovirulence testing of the two candidate bulks, both 2018 candidates displayed limited virulence, with paralysis rates that are the same or lower than rates observed with the 2016 material. Further testing of the candidates is ongoing, including monkey neurovirulence testing and confirmation of temperature sensitivity, and the use of 2018 candidates will only be initiated when the results of these tests are known and confirm the relative safety of both vaccine lots.

Deep sequencing analyses of the 2016 candidate 2 lot and the 2018 lots provides supportive information to the neurovirulence testing, including that (1) the modified sites incorporated in the candidates are preserved and (2) there are no detected mutations in domain V of the virus, the primary attenuation site for Sabin-derived strains. As anticipated, there were some noted changes from the 2016 preparations, which included a reduction in the level of one variant (VP1 E295K) for both candidates. Increases in levels of other variants were noted including low levels (1–2%) of a VP1-143 reversion in candidate 1. This reversion occurs readily in replication *in vivo* for Sabin-2 and also was observed in both candidates in shed virus samples from the M4a trial. The increases in these variants are not expected to impact safety (as confirmed by mouse and monkey neurovirulence testing) or immunogenicity.

### **6.3 OTHER MEDICATION ADMINISTERED IN THE STUDY**

Other vaccines are routine childhood vaccines administered according to the manufacturer's instructions.

### **6.4 PACKAGING AND LABELING**

Both vaccine candidates are labelled and packed according to local law and regulatory requirements.

Detailed information on the packaging and labeling is specified in **the nOPV2 Handling and Storage Instructions for the study**.

## 6.5 STORAGE AND VACCINE ACCOUNTABILITY

The Investigator (or his/her designee) is responsible for the safe storage of all study vaccine assigned to the clinical site, in a locked, secure storage facility with access limited to those individuals authorized to dispense the study vaccine, and maintained within the appropriate ranges of temperature. All study vaccine must be stored as specified at delivery and in the original packaging.

The nOPV2 candidate vaccines should be stored in a freezer at approximately  $-20^{\circ}\text{C}$  ( $\pm 5^{\circ}\text{C}$ ). After thawing, the vaccine can be stored at  $+2$  to  $+8^{\circ}\text{C}$  for up to 2 weeks. **Once opened a vial must be used within 48 hours, when it expires.**

Regular temperature logging of the study vaccine storage room at the clinical site should be performed. In case a deviation in storage conditions should occur, the clinical site must not further dispense the affected study vaccine and notify the Sponsor.

The Investigator is responsible for ensuring that all study vaccines received at the clinical site are inventoried and accounted for throughout the study.

Study vaccine should be dispensed under the supervision of the Investigator, a qualified member of the clinical staff, or by a hospital/clinic pharmacist. The Investigator must maintain accurate records demonstrating date and amount of vaccine administered to and by whom. Study vaccines will be supplied only to subjects participating in the study.

The Sponsor's designated site monitor will periodically check the supplies of study vaccines held by the Investigator or pharmacist to ensure accountability and appropriate storage conditions of all study vaccine used.

Unused study vaccine must be available for verification by the site monitor during on-site monitoring visits. After the last visit of the last subject in the study (LSLV), any used and unused study vaccine will be returned to the Sponsor, or destroyed at the clinical site with the Sponsor's written permission (in this case a certificate of destruction will be provided and filed in the Trial Master File [TMF]).

## 6.6 RANDOMIZATION AND BLINDING

All subjects will receive one of the **three** nOPV2 candidate **lots**.

**In Stage I, 1–5 year-old OPV-IPV pre-vaccinated subjects in Cohort A will be enrolled to receive two  $10^6$  CCID50 doses (N=50) of nOPV2 candidate 2 lot 2016: Group A2H2[2016].**

Following DSMB approval previously enrolled infants in Cohort B at 18–22 weeks of age who have received 3 doses of bOPV and 1 dose of IPV will be assigned to **Group B2L1[2016]** (N=162) to receive one  $10^5$  CCID50 dose of nOPV2 candidate 2 (2016). A randomly selected sub-group (N=50) will receive a second dose of this vaccine 28 days after the first: **Group B2L2[2016]**. After the DSMB have considered the safety data from the first fifty participants in Group B2L1[2016] and given approval, the following group of 18–22 week-old infants (N=162) will then be assigned to receive one  $10^6$  CCID50 dose of nOPV2 candidate 2: **Group B2H1[2016]**, and a randomly selected sub-group (N=50) will receive a second dose of this vaccine 28 days after the first: **Group B2H2[2016]**.

**In Stage II**, this procedure will be repeated with the 2018 lots of candidates 1 and 2:

Initially 100 OPV-IPV pre-vaccinated Cohort A subjects will be enrolled and randomized to two equal groups to receive two  $10^6$  CCID50 doses (N=50) of nOPV2 candidate 1 (**Group A1H2[2018]**) or nOPV2 candidate 2 (**Group A2H2[2018]**).

Enrollment of Stage II 1 to 5 year-olds may proceed upon completion of Stage I, i.e. complete enrolment and the availability of a minimum of 14 days safety follow-up in at least 50 subjects of group **B2H2[2016]** after administration of  $10^6$  CCID50 nOPV2 (2016), regardless of the enrollment status of the 2016 infant cohort.

Following DSMB approval infants enrolled in Cohort B at 18–22 weeks of age after receiving 3 doses of bOPV and 1 dose of IPV will be randomly assigned to **Group B1L1[2018]** (N=162) to receive one  $10^5$  CCID50 dose of nOPV2 candidate 1 (2018) or **Group B2L1[2018]** (N=162) to receive one  $10^5$  CCID50 dose of nOPV2 candidate 2 (2018). Randomly selected sub-groups (N=50) will receive a second dose of the respective vaccine 28 days after the first: **Group B1L2[2018]** and **Group B2L2[2018]**.

After the DSMB have given approval based on consideration of the safety data from the first fifty participants in each **Groups B1L2[2018]** and **B2L2[2018]**, the following groups of 18–22 week-old infants (N=162) will then be assigned to receive either one  $10^6$  CCID50 dose of nOPV2 candidate 1 (2018): **Group B1H1[2018]**, or one  $10^6$  CCID50 dose of nOPV2 candidate 2 (2018): **Group B2H1[2018]**, and randomly selected sub-group (N=50) will receive a second dose of the respective vaccines 28 days after the first: **Groups B1H2[2018]** and **Group B2H2[2018]**. Enrollment of subjects into infant groups in Stage II may proceed to build up the cohorts and to receive their three doses of bOPV and one dose of IPV, but they will not receive any nOPV2 candidate until receipt of a positive recommendation from the DSMB based on safety data from Stage I.

Allocation of each subject in Stage II from Cohorts A and B, within candidate and dose level groups to the different one-dose or two-dose candidate groups will be described in a computer-generated randomization schedule prepared prior to start of the study by Assign Data Management and Biostatistics GmbH, [name] using SAS® software (SAS Institute Inc., Cary, NC, USA).

The randomization will be balanced using randomly permuted blocks across the groups.

## 6.7 DOSE AND ADMINISTRATION

For all lots (2016 and 2018) one  $10^5$  CCID50 dose of vaccine (0.1 ml) is contained in two drops, which are delivered using the dropper supplied with the vaccine.

For the 2016 lot of candidate 2 one  $10^6$  CCID50 dose of vaccine (0.3 ml) is contained in six drops, which are delivered using the dropper supplied with the vaccine.

For both 2018 lots (candidates 1 and 2) one  $10^6$  CCID50 dose of vaccine is contained in 1.0 ml which may be delivered from a syringe, or using a syringe to measure the dose into a spoon.

The vaccinees will remain under medical supervision for at least 30 min following the administration of each vaccine.

## **6.8 COMPLIANCE**

All vaccine administrations in the study will be supervised by the Investigator or his/her designee.

## **7. PRIOR AND CONCOMITANT THERAPY**

All therapies (prescriptions and over-the-counter medications) other than the study vaccine administered from informed consent until the last study visit must be recorded in the source documents and in the concomitant therapy section of the electronic case report form (eCRF) (name of the drug, dosage, route and dates of administration).

The Sponsor must be notified in advance (or as soon as possible thereafter) of any instances in which prohibited therapies are administered. In the older age Cohort (Group A), subjects are not allowed to receive any other vaccines during the whole study period and 4 weeks prior to study vaccination. Influenza vaccine will be allowed in all groups according to National Immunization Recommendations.

There will be no restrictions in using concomitant therapies except for any medication that has a potential effect on the immune system in the opinion of the Investigator.

Infants in Cohort B will concomitantly receive with bOPV/IPV the DTPw-HB-Hib, Pneumococcal conjugate and Rotavirus vaccines which will be provided by the Sponsor and the local National Immunization Program. In infants who receive nOPV2 at 18-22 weeks, no other vaccines can be administered 3 weeks before or 72 days after nOPV2 with the exception of influenza vaccine according to the National Immunization Program.

## **8. ASSESSMENTS**

### **8.1 TIMING OF ASSESSMENTS**

An overview of the timing of vaccine administration and assessments is given in the Time and Events Schedules.

Parent(s)/guardian(s) will be given a full explanation of the nature of the study and written informed consent (approved by the local ethics committee) will be obtained from parent(s)/guardian(s) according to local requirements before any study-related assessment will be carried out.

Adverse events and the intake of concomitant medication will be monitored continuously from informed consent until the last study-related activity 28 days after the last vaccination. Any subsequent SAEs and IMEs occurring up to six months after the last vaccination will be solicited by telephone contact with parents.

After the pre-dose procedures, including recruitment, administration of routine vaccinations and collection of baseline information and biological samples outlined in the Time and Events Schedule, the subjects will receive the first dose of study vaccine according to the procedure described in Section 6.6, followed by further assessments as outlined in the Time and Events Schedules. The subjects will be kept under medical supervision for at least 30 minutes after vaccination.

An electronic diary card and a thermometer will be distributed to parent(s)/guardian(s) and their use will be explained. Paper diary cards could be used as back up.

Unscheduled visits can be planned for instance:

- To obtain additional information to ensure safety to the subject. Additional blood and urine samples may be taken at the discretion of the Investigator.

Findings made during unscheduled visits should be reported in the source documents and in the designated sections of the eCRF.

### **8.2 IMMUNOGENICITY**

#### **8.2.1 *Immunogenicity Variables***

##### ***Neutralizing Type 2 Poliovirus Antibody Titers***

Blood samples for the determination of neutralizing type 2 poliovirus antibodies will be taken at the time points specified in the Time and Events Schedules. Neutralizing antibodies against type 2 poliovirus will be determined using a sero-neutralization assay.

Detailed descriptions of the collection, handling, transport and processing of the blood samples will be included in the laboratory manual.

Samples that remain after protocol-specific assessments have been performed may be used for further exploratory work on polio, including cryofreezing for future immunological studies. No human DNA or RNA analysis will be performed.

### ***Immunogenicity criteria***

For an overview of endpoints, see Section 3.

The following endpoints will be based on neutralizing type 2 poliovirus antibody titers:

- Median and geometric mean titers.
- Sero-protection: defined as poliovirus type 2-specific titers  $\geq 1:8$ .
- Sero-conversion: defined as a change from seronegative to seropositive, and in seropositive subjects, as an antibody titer increase of  $\geq 4$  fold over baseline, corrected for maternal antibody titer where applicable/age-appropriate. **Seroconversion will be computed from Day 0 for all subjects, and from Day -84 for infant subjects.**

### **8.3 VIRAL SHEDDING**

Stool samples will be collected at the time points outlined in the Time and Events Schedule. As a measure of intestinal immunity, shedding of type 2 poliovirus in a pre-selected subset of stools will be evaluated using:

- RT-PCR (viral identity).
- CCID50 determination (titer).

Detailed descriptions of the collection, handling, transport and processing of the stool samples will be included in the laboratory manual.

### **8.4 NEUROVIRULENCE**

Phenotypic neurovirulence of shed virus will be evaluated in a subset of stool samples, using a transgenic mice assay (TgPVR mice). Stool samples collected for viral extraction will be collected as outlined in the Time and Events Schedule and stored.

For the neurovirulence testing of virus derived from stool samples of clinical trial participants vaccinated with oral polio vaccines, a modified transgenic mouse neurovirulence test (mTgmNVT) may be applied. The TgmNVT that will be used is adapted from the WHO SOP (Neurovirulence Testing of Oral Polio Vaccine Using TgPVR21 Transgenic Mice) used for vaccine release. In the mTgmNVT, blinded, cell culture-amplified virus material (from stool) is titrated and then diluted to a fixed target dose/inoculum selected to detect reversion of the Sabin-2 strain. The inoculum is intraspinally injected into transgenic mice susceptible to poliovirus. Control virus is tested concurrently in the TgmNVT to assess the validity of a given test.

The inoculated mice are observed daily for the presence of clinical signs of poliovirus infection (weakness, paresis, and paralysis). After the observation period of 14 days, the in-vivo phase is ended. Mice are euthanized and a clinical end score (paralyzed or non-paralyzed) is assigned to each mouse. Results are reported as percent paralysis observed per sample. Samples that induce paralysis above a critical threshold may be further tested in a multi-dose format of the TgmNVT for further characterization.

NV data from this study will be combined with data from the historical control study (M2) to draw comparisons between shed virus from Sabin-2 and the **2018 lots of novel vaccine candidates.**

Stool samples that remain after protocol-specific assessments have been performed may be used for further exploratory work on polio. No human DNA or RNA analysis will be performed.

## **8.5 SAFETY EVALUATIONS**

The safety assessment in this study will be based on AEs and clinical laboratory tests, as described in the following sections.

### **8.5.1 *Adverse Events***

Adverse events will be monitored continuously from the time of informed consent signature until the last study-related activity 28 days after the last vaccination. Any subsequent SAEs and IMEs occurring up to six months after the last vaccination will be solicited by telephone contact with parents. At regular intervals during the study, parents will be asked non-leading questions to determine the occurrence of any AEs. All AEs reported spontaneously during the course of the study will be recorded as well.

For detailed definitions and reporting procedures of AEs, see Section 11.

Solicited AEs will be recorded for 7 days following each vaccine dose of study vaccine using a Diary Card.

### **8.5.2 *Clinical Laboratory Tests***

Blood samples of up to 6 mL in both Cohorts will be collected at the time points indicated in the Time and Events Schedules.

Standard laboratory tests as outlined in Appendix 1 will be performed by a local laboratory.

The Investigator must review the laboratory report, document this review, and record any change occurring during the study he/she considers to be clinically relevant in the source documents and in the AE section of the eCRF. Laboratory values outside the normal range will be flagged and their clinical relevance will be assessed by the Investigator. A copy of all laboratory reports must be filed in the subject's medical records.

Samples that remain after protocol-specific assessments have been performed may be used for further exploratory work on polio, including cryofreezing for future immunological studies. No human DNA or RNA analysis will be performed.

## **8.6 EXPLORATORY EVALUATIONS**

### **8.6.1 *Sequencing***

Viral sequencing methods (e.g. deep sequencing) may be performed on selected stool samples taken at one or more of the time points specified in the Time and Events Schedule to explore the heterogeneity of shed virus, including reversion at known sites of attenuation, as well as attenuating modifications introduced to enhance genetic stability. Sequence information on shed virus may be compared with the results of neurovirulence testing, if available.

## **8.7 APPROPRIATENESS OF MEASUREMENTS**

The assessments which will be made in this study are either standard or are scientifically justified.

Each biological assay contains a reference material used as a control. Additional re-test of some samples may be conducted to ascertain the presence of temporal variability in assay results.

## **9. STUDY TERMINATION/COMPLETION**

### **9.1 STUDY COMPLETION**

#### ***9.1.1 Subject Completion***

A subject will be considered to have completed the study if all study related procedures have been completed for them 28 days after the last study vaccination and they are not withdrawn before the final study safety visit 6 months after their last vaccination.

#### ***9.1.2 Study Completion Date***

The study completion date is considered to be the date on which the final serologic analysis is available for the purpose of assessing the primary immunogenicity objective, i.e. the proportions of the B cohort infant groups with seroprotective type 2 polio neutralizing antibodies at Day 28 following the first doses of the two nOPV2 candidates at both dose levels.

### **9.2 REMOVAL OF SUBJECTS FROM STUDY OR INVESTIGATIONAL PRODUCT**

#### ***9.2.1 Removal from Study***

Parents(s)/guardian(s) have the right to withdraw subjects from the study at any time for any reason, including personal reasons. A subject can be withdrawn without giving a reason. The Investigator should however try to find out why a subject is withdrawn from the study and document the reason for withdrawal in the source documents and on the eCRF.

Subjects **may** be withdrawn from the study in the event of:

- A severe AE or a SAE;
- Difficulties in obtaining blood or other samples;
- Failure of the subject and/or subject's parent(s)/guardian(s) to comply with the protocol requirements or to cooperate with the Investigator.

Subjects **must** be withdrawn from the study in the event of:

- Withdrawal of consent by parent(s)/guardian(s);
- For safety reasons, if, in the Investigator's opinion, in the best interest of the subject.

In the event of a subject being withdrawn from the study, the monitor and Sponsor should be informed: in the event of withdrawal due to an SAE (for details on AE reporting see Section 11), the Sponsor should be notified within 24 hours; in the event of withdrawal for other reasons; the Sponsor should be notified within 2 days from the event.

If there is a medical reason for withdrawal, the subject will remain under the supervision of the Investigator until satisfactory health has returned.

Subjects who are withdrawn from the study prior to completion of the scheduled study procedures for any reason (e.g. AE, withdrawal of consent) should be invited to complete the assessments as much as possible: as long as the subjects' parent(s)/guardian(s) consents, all relevant assessments of the day on which the subject withdrew from the study should be completed, at least those related to safety. In case of an AE, the appropriate follow-up will be done.

Subjects who are withdrawn from the study will not be replaced.

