## **TIME AND EVENTS SCHEDULE – ONE DOSE INFANT GROUPS**

Assessments	Groups B1L1[2018], B2L1[2016], B2L1[2018], B1H1[2018], B2H1[2016] and B2H1[2018]									Follow-up phone contact
	bOPV-IPV pre-vaccination phase			Study vaccination phase						
Visit	-3	-2	-1	1	2	3	4	5	6	
Time of Visit (days) Visit Window	D -84 (+14,-7 days)	D -56 (±7 days)	D -28 (±7 days)	D 0	D 7 (± 2 days)	D 14 (± 3 days)	D 21 (± 2 days)	D 28 a (+ 2 days)	D 180 (± 14 days)	
Informed consent b	X									
In-/exclusion criteria	X			X						
Medical history/concomitant diseases	X			X						
Medication/Vaccination history c	X			X						
Demographic data	X			X						
Physical examination	X			X	X			X		
Clinical laboratory tests d				X e	X			X		
Randomization for one dose only				X						
Administration of bOPV f	X	X	X							
Administration of IPV f			X							
Administration of nOPV2 f				X g						
Serum sample for polio antibodies	X e			X e	X			X		
Stool sample for viral culture/quantitative PCR, stool sample for potential poliovirus sequencing, stool sample for potential neurovirulence				X-----X h		X	X	X		
Solicited systemic AEs (Diary) i				X-----X						
Remote contact for safety follow-up j				X-----X					X	
Concomitant therapies k				X	X	X	X	X	X	
Adverse events k				X	X	X	X	X	X l	

- a. In case of early termination the subjects will be asked to return to the clinical site within 14 days after discontinuation for assessments as outlined on Day 28.  
b. No study-related assessment is to be carried out before signing the informed consent form.

- c. Including polio vaccination history.
- d. For a list of assessments, please see Appendix 1: Overview of Laboratory Assessments.
- e. Prior to vaccination. Samples at V1 (day 0) will also be used to assess anti-HBs and anti-Hib antibodies.
- f. The subjects will be kept under medical supervision for at least 30 min after vaccination. The subjects will concomitantly receive DTPw-HB-Hib vaccine at V-3, V-2 and V-1, pneumococcal conjugate vaccine at V-3 and V-1 and rotavirus vaccine at V-3 and V-1.

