### **9.2.2 *Removal from Investigational Product***

Removal from investigational product administration concerns subjects who do not receive a complete study vaccination schedule as planned per protocol. A subject who is withdrawn from further study vaccine administration need not necessarily be withdrawn from the study as further study procedures or follow-up may be performed (safety or immunogenicity) if planned in the study protocol.

Information pertaining to premature discontinuation of the study vaccine will be documented in the eCRF. The Investigator will document whether the decision to discontinue further vaccination was made by the subjects' parent(s)/guardian(s) or the Investigator, and which of the following possible reasons was responsible for withdrawal:

- SAE/IME.
- AE.
- Other (specify).

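### Section 9.2.1 allows removal from the whole study for a severe AE or SAE, and nothing then keeps the six-month SAE/IME contact or, for early removals, an on-window Day 28 serum

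*Combined protocol and SAP*

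**What the plan says.** Section 9.2.1 has two lists. Withdrawal is mandatory when consent is withdrawn, or when the investigator judges on safety grounds that it is in the child's best interest. Withdrawal is optional for three other reasons, the first being "A severe AE or a SAE", with no condition on causality. Withdrawn children are not replaced.

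After withdrawal, with parental consent, "all relevant assessments of the day on which the subject withdrew from the study should be completed, at least those related to safety". The section adds "In case of an AE, the appropriate follow-up will be done" and, where the reason is medical, "the subject will remain under the supervision of the Investigator until satisfactory health has returned". Section 11.6 follows recorded AEs to resolution, stabilization or database lock.

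The schedule for one-dose infants asks early-terminated children to "return to the clinical site within 14 days after discontinuation for assessments as outlined on Day 28". The schedules for two-dose infants and for 1 to 5 year-olds do the same for the Day 56 assessments. Both sets of assessments include serum.

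On long-term safety, Section 8.5.1 says: "Any subsequent SAEs and IMEs occurring up to six months after the last vaccination will be solicited by telephone contact with parents". Section 8.1 repeats this, and the schedules place the contact at Day 180 (one dose) or Day 208 (two doses). The primary safety endpoint in Section 3.1 covers the time from consent to the end of the study.

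Three other sections bear on the point:

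- Section 5.4, for a child due a second dose who has a listed contraindication, including a causally related serious, grade 3 or important medical event: "the subject should not receive the second dose of vaccine but may continue other study procedures at the discretion of the Investigator". Its closing sentence then says, without qualification, that the child is followed to resolution and for the immune response.
- Section 9.2.2: "A subject who is withdrawn from further study vaccine administration need not necessarily be withdrawn from the study".
- Section 5.3 keeps children with clinically relevant laboratory deviations in the study for safety follow-up, without further doses.

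**The concern.** A severe or serious event is part of what the safety objective measures. If such an event can end participation, the time during which later events are looked for depends on an earlier event of the same kind. The trigger need not be vaccine-related. A child removed after an unrelated SAE could therefore have a first causally related event later, at a time when no contact is scheduled to find it. The child would stay in the Total Vaccinated denominator with shortened observation. For a live vaccine under surveillance for acute flaccid paralysis, the months after Day 28 matter.

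The Day 28 seroprotection endpoint is also exposed, to a lesser degree. Immunogenicity is analysed primarily per protocol, withdrawn children are not replaced, and Section 10.1.9 names no specific missing-data method.

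**Working it through.** **1. The plan's own figures.** Inputs from Section 10.2: 129 evaluable infants per candidate and dose level, 91 M2 controls, 95% seroprotection in both, margin 10 points, one-sided alpha 0.025, 20% dropout. Power is the sum, over all pairs of counts, of Bin(129, 0.95) × Bin(91, 0.95) wherever the Miettinen-Nurminen score statistic is at least 1.96. This gives 90.4%, matching the stated 90%. Enrollment is 129 / 0.80 = 161.25, so 162, as stated.

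**2. Day 28 window, one-dose infants.** The visit window is Day 28 to Day 30. A child withdrawn on Day d returns by Day d + 14 at the latest. An on-window serum needs d + 14 ≥ 28, so d ≥ 14. Removal before Day 14 gives a serum, but an early one. The plan does not settle in advance whether it would count: Section 10.1.1 leaves deviations to be classed as minor or major before database lock.

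**3. Safety time without a scheduled contact, one-dose infants.** The contact is at Day 180.

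- Removed Day 3: last visit by Day 17; (180 − 17) / 180 = 163/180 = 90.6%.
- Removed Day 14: last visit by Day 28; (180 − 28) / 180 = 152/180 = 84.4%.

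The triggering event is still followed in this time. What is missing is scheduled enquiry about new events.

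**4. Conflict with Section 5.4.** The closing sentence of 5.4 requires follow-up, including for the immune response, in children due a second dose who have a causally related severe or serious event. Section 9.2.1 lets the same child leave the study. The groups in which this could arise hold 6 × 50 infants + 3 × 50 older children = 450. That is the scope of the rule, not a count of children affected.

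**5. Children eligible for removal.** The documents give no severe AE or SAE rate. Assumed rates of 1%, 2% and 5% give 162 × 0.01 = 1.6, 162 × 0.02 = 3.2 and 162 × 0.05 = 8.1 infants per group. Removal is optional, so fewer would actually leave.

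**6. Effect on the seroprotection comparison.** Repeating step 1 with 1, 2, 3, 5 or 8 of the 129 lost gives power between 87.8% and 89.3%. Exact power is saw-toothed, so it does not fall steadily. For bias, take the extreme case in which all k lost infants are non-protected and the observed rate is 95%. The overstatement is 0.95 − 0.95 × 129 / (129 + k):

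| k | Overstatement (points) |
|---|---|
| 1 | 0.7 |
| 2 | 1.5 |
| 3 | 2.2 |
| 5 | 3.5 |

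The margin is 10 points.

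**The case against.** The strongest reply is that the rule is optional and well cushioned. Section 9.2.1 says such children *may* be withdrawn and invites them to complete as much as possible. The return visit includes serum, which is on-window if removal is on Day 14 or later. The triggering event is already recorded and counted, and it is followed to its outcome. The 20% dropout allowance is not limited by cause. All of this stands, and it limits the size of the problem. It does not fill the gap: the invitation is spelled out as the assessments of the withdrawal day, and neither it nor the footnotes reach the six-month contact.

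A reader might infer more than the documents support:

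- **That Section 9.2.2 contradicts 9.2.1.** Both are permissive and can hold together. Section 5.4 also leaves other procedures to discretion; only its closing sentence conflicts, and it does not cover one-dose infants.
- **That all 6 × 112 = 672 one-dose infants are affected.** They are the infants with no further nOPV2 dose to withhold. An affected infant must have a severe or serious event and then be removed at discretion. Also, 2 × 112 = 224 of them received the 2016 lot and are outside the primary immunogenicity comparison.
- **That both co-primary endpoints are biased.** For safety, only events after removal can be missed. For seroprotection, bias needs infants with severe events to respond differently, and nothing in the documents says they do. M2's withdrawal rules are not given, so a difference from M2 cannot be asserted either.
- **That sampling difficulty should also go as a ground for withdrawal.** No passage conflicts with it.

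**Conclusion.** The point holds in a limited form. An AE-related removal under Section 9.2.1 can end scheduled SAE/IME ascertainment well before six months, in children who have already had a severe or serious event. In one-dose infants removed before Day 14, it also puts the serum ahead of the Day 28 window. The rule conflicts with the closing sentence of Section 5.4 for two-dose children with a causally related event, and sits poorly with Section 5.3.

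The size cannot be fixed from the documents. The 1.6 to 8.1 eligible infants per group rest on assumed rates of 1% to 5%. The power figures rest on assumed losses of up to 8 infants, and the overstatement of 0.7 to 3.5 points on losses of one to five, all non-protected. The sample size of 129 evaluable and 162 enrolled needs no change. The main reason to act is completeness of safety follow-up.

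**What to change.** Reconcile Sections 5.4, 9.2.1, 9.2.2 and the early-termination footnotes. State that a child removed because of a severe AE or SAE is still asked for the scheduled Day 28 (or Day 56) serum and for the Day 180 (or Day 208) SAE/IME contact, unless consent is withdrawn or the best-interest clause applies. Leave the best-interest clause and the sampling-difficulty ground as they are. The change concerns data collection only and touches no dosing or treatment rule.

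The cost is amended wording and a few contacts, already in the schedule, kept for a small number of children.
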